**Table 1: Schedule of Visits and Procedures Dose Escalation (Phase 1) (Cont'd)**

Assessment Period	Screening	Cycle 1 and Cycle 2													Cycle 3 and Beyond			Post-treatment	
Study Days a	Day -28 to -1	Day 1	Day 2	Day 3	Day 4	Day 5	Day 6	Day 7	Day 8	Day 9	Day 10	Day 11	Day 15	Day 22b	Day 1	Day 8	Day 22 b	End of Treatment (+10 days)	Follow-up 3 mo
Administer fluids and advise patients aa		X	X	X	X	X									Days 1-5				
NKTR-214 administration bb		X													X				
Quarterly follow-up																			X

Footnotes:

- a. The acceptable visit window is + 1 days for Day 11 and ±1 day for Day 8 and Day 15 and ± 7 days for the follow-up visit post-treatment. Visits may be skipped or postponed if prospectively identified by the Investigator (e.g., national holidays, subject vacations). If Day 4 visit is missed then Day 4 assessments must be done at the next in-clinic visit. All procedures and examinations should be performed before the administration of study drug(s), except as indicated below.
- b. Assessments only applicable if dosing cycle is changed to 28-day cycle.
- c. The Institutional Review Board (IRB)-approved informed consent form (ICF) must be signed before any study-specific procedures or examinations are performed.
- d. An event occurring after the subject has provided informed consent, but before the first dose of study treatment, will be collected as medical history unless the event is either new and attributed to protocol-mandated procedures by the Investigator OR there is a significant change in the rate of occurrence or an increase in the severity of the pre-existing condition which is judged to be clinically important and attributed to the protocol-mandated procedures by the Investigator. Any new or clinically significant changes in the subject’s medical and/or cancer history that occur immediately after the first dose of drug will be recorded as AEs.
- e. Include prior cancer treatments: previous immunotherapy, chemotherapy, targeted therapy, radiation, OTC medications, herbs and dietary supplements.

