- x. Biomarker sample will be drawn prior to dose on Day 1 and on Day 8  $\pm 3$  days. In addition, biomarker samples will be collected prior to dose on Day 1 of Cycle 3 and all odd-numbered cycles thereafter (e.g., Cycles 3, 5, 7, etc.). If the optional tumor biopsy at disease progression is collected, collect an additional biomarker sample at the same time.
- y. Blood samples (2 mL) for PK analyses will be collected in all cycles, with more intense sampling in Cycles 1 and 2. PK sample times are as follows: Cycle 1 and Cycle 2 Day 1: predose, end of administration (EOA  $\pm 2$  min), 0.5 hr  $\pm 5$  min, 3 hr  $\pm 10$  min, 6 hr  $\pm 2$  hr, and 2, 3, 4, 5, 8, 11, and 15 days postdose. Cycle  $\geq 3$ : predose, EOA ( $\pm 2$  min), Day 8, and End of Treatment. On Days 2 and 3 of Cycles 1 and 2, 4 mL of blood will be drawn instead of the usual 2 mL. The blood draws should occur as close to 30 or 38 hours post dose as possible.
- z. In the event of a possible study-drug-related SAE throughout the study, additional PK blood samples may be drawn as close to the event as possible to help characterize any possible relationships between drug exposure and the clinical event.
- aa. Administer at least 2 liters of fluid (IV or self-administered orally [e.g., fluid containing electrolytes]) for Days 1 to 5 of every cycle. Advise subjects to restrain from strenuous activity and avoid long hot showers and saunas for Days 1 to 5 of every cycle. A Patient Wallet Card is available that contains important safety information.
- bb. Administer NKTR-214 at the subject's assigned dose level as an intravenous infusion over 15 minutes  $\pm 5$  minutes.

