- w. Biomarker sample drawn prior to dose on Day 1 and on Day 8 ± 3 days. In addition, biomarker samples will be collected prior to dose on Day 1 of Cycle 3 and all odd-numbered cycles thereafter (e.g., Cycles 3, 5, 7, etc.). If the optional tumor biopsy at disease progression is collected, collect an additional biomarker sample at the same time.
- x. Stool sample to be collected prior to Cycle 1 Day 1.
- y. Blood samples (2 mL) for PK analyses will be collected in all cycles, with more intense sampling in Cycles 1 and 2. PK sample times are as follows: Cycles 1 and 2 Day 1: predose, end of administration (EOA ± 2 min), 0.5 hr ± 5 min, 3 hr ± 10 min, 6 hr + 2 hr, and 2, 3, 4, 5, 8, 11, and 15 days postdose. Cycle ≥ 3: predose, EOA ± 5 mins, Day 8 and End of Treatment.
- z. In the event of a possible study drug-related SAE throughout the study, additional PK blood samples will be drawn as close to the event as possible to help characterize any possible relationships between drug exposure and the clinical event.
- aa. Administer at least 2 liters of fluid (IV or self-administered orally [e.g., fluid containing electrolytes]) for Days 1 to 5 of every cycle. Advise subjects to restrain from strenuous activity and avoid long hot showers and saunas for Days 1 to 5 of every cycle. A Patient Wallet Card is available that contains important safety information.
- bb. Administer NKTR-214 at the subject's assigned dose level as an intravenous infusion over 15 min ± 5 min.

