### 2.2.3 Toxicology

The safety of NKTR-214 was evaluated in rats and cynomolgus monkeys for up to 6 weeks of every 14 day (q14d) administration (q14dx3). A PEG control was included in the rat GLP toxicity study. Biomarkers of NKTR-214 immune stimulation (peripheral lymphocyte counts and plasma sCD25 levels) were included in these studies. In addition, cardiovascular safety was evaluated in a telemetry study in cynomolgus monkeys. The monkey was identified as the most sensitive species (see Table 3). In addition, NKTR-214 binding affinity to the IL-2 receptor and T-cell activation was comparable in vitro between human cell lines and the cynomolgus monkey cell lines. Clinical observations in the monkey after each NKTR-214 dose included transient (and reversible) hypoactivity, decreased appetite, emesis, diarrhea, decreased fecal output, and hunched posture on Days 2-9 after each dose. Findings consistent with systemic immune

stimulation included transient and dose-related increased white blood cell (WBC) counts, largely due to the increase in lymphocytes, and an increase in sCD25 that were observed 5 to 7 days post each NKTR-214 dose, all of which returned to baseline 14 days postdose. Noteworthy histopathology findings in the monkey were minimal to mild inflammation in multiple organs (including liver, heart, and kidney), hematopoiesis in bone marrow, and hypercellularity in the thymus and spleen. These histopathologic changes partially or in some cases completely resolved on recovery (6 weeks post last dose). Of note, no evidence of cardiovascular effects such as ECG abnormalities, hypotension, pulmonary edema or vascular leak were found in the monkey at the NKTR-214 maximum tolerated dose (MTD) of 0.1 mg/kg in contrast to the reports of vascular leak at the MTD for aldesleukin ([Anderson, 1993](#)). The MTD of NKTR-214 was determined as 0.3 mg/kg in rats and 0.1 mg/kg in monkeys. Detailed descriptions of these studies and their results can be found in the NKTR-214 Investigator’s Brochure.

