### 2.3 Starting Dose Rationale

The planned Phase 1 NKTR-214 starting dose of 0.003 mg/kg is 1/10th of the cynomolgus monkey MTD (0.1 mg/kg) that has been corrected for body surface area. A dose of 0.003 mg/kg is expected to be active in humans since it is the lowest dose tested in the monkey toxicology study at which increases in both sCD25 (10-fold) and lymphocyte counts (2-fold) were observed. A dosing schedule of q21d was chosen for the first in human study based on the histopathologic changes (inflammatory cell infiltrates) in monkeys 14 days after administration of the last q14d NKTR-214 dose that almost completely resolved with an additional 4 weeks of recovery (6 weeks following the last dose). [Table 3](#) shows the safety margins for the proposed clinical starting dose of NKTR-214.

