#### 4.1.2.2 Part 2: Dose Expansion Scheme

At least 1 study Investigator and the Sponsor Medical Monitor will meet and decide the dose to be studied in Part 2 before the initiation of the dose expansion cohort (either the MTD dose or dose lower than MTD). This dose will be the recommended Phase 2 dose (RP2D), and all subjects in the expansion cohort will receive this dose. The RP2D may also be determined based on a biological effect of the study drug as determined by anti-tumor activity and immune activation. The RP2D for dose expansion will be communicated via an administrative dosing letter and enrollment in the expansion phase may begin without a protocol amendment.

Approximately 50 subjects with renal cell carcinoma (RCC) will be enrolled into Part 2. Subjects in the expansion cohort will be treated until tumor progression (treatment may continue if there is clinical benefit), death, unacceptable toxicity, symptomatic deterioration, achievement of maximal response, subject choice, the Investigator's decision to discontinue treatment, the subject withdraws consent, or Nektar Therapeutics decides to terminate the trial.

Note: The sponsor reserves the right to evaluate two doses or two dosing schedules in each expansion cohort if necessary based on the safety profile during the dose escalation portion.

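### The ± 3 day tolerance on the Day 8 blood biomarker sample adds avoidable timing noise to small-cohort comparisons of immune activation, at a visit already held to ± 1 day

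*Protocol*

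**What the plan says.** **Sampling window.** For dose escalation, Table 1 footnote x reads "Biomarker sample will be drawn prior to dose on Day 1 and on Day 8", followed by a tolerance of ± 3 days. For dose expansion, Table 2 footnote w has the same rule: "Biomarker sample drawn prior to dose on Day 1 and on Day 8 ± 3 days". Apart from this draw, the footnotes name pre-dose samples on Day 1 of Cycle 3 and later odd-numbered cycles, and an extra sample if the optional progression biopsy is taken. The Day 8 draw is therefore the only routine early post-dose blood biomarker sample that they name.

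**Visit window.** Table 1 footnote a reads "The acceptable visit window is + 1 days for Day 11 and ±1 day for Day 8 and Day 15". Table 2 footnote a sets the same limits.

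**Expected time course.** Protocol Section 2.2.3 describes, in monkeys, a transient lymphocyte-driven rise in white cells and "an increase in sCD25 that were observed 5 to 7 days post each NKTR-214 dose, all of which returned to baseline 14 days postdose". Section 2.3 adds that at 0.003 mg/kg in the monkey "increases in both sCD25 (10-fold) and lymphocyte counts (2-fold) were observed".

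**Use of the data.** Protocol Section 4.1.2.2 states: "The RP2D may also be determined based on a biological effect of the study drug as determined by anti-tumor activity and immune activation". Section 4.1.2.1 enrols at least 3 subjects per escalation cohort.

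**Handling of sampling time.** Section 6.6 requires the date and actual time of every PK sample. Sections 6.8 and 6.8.1 have no matching sentence for biomarker samples and refer to a Laboratory Manual. The synopsis plans biomarker values and changes from screening at each observation time, without saying whether that time is nominal or actual. SAP Section 12, on exploratory analyses, is still to be written.

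**The concern.** A sample labelled Day 8 may be drawn on any of Days 5 to 11. Days 5, 8 and 11 are all scheduled visits in Cycles 1 and 2, so the extra width can be used in practice. If the human immune response is as brief as the monkey response, two subjects with the same true response can give different Day 8 readings only because one was sampled near the peak and the other was not.

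In a cohort of 3, one or two off-peak samples can move the cohort summary visibly. The sponsor may look at immune activation across dose levels when choosing the recommended Phase 2 dose. Timing noise could then blur a real difference between adjacent doses or suggest one that is not there. No planned analysis takes the actual sampling day into account.

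**Working it through.** The documents give no precision or sample size for biomarker comparisons, so there is no plan figure to reproduce. The check is day arithmetic plus a sensitivity calculation on an assumed profile.

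**1. Day arithmetic** (days after dose = study day − 1)

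- Biomarker draw: 8 ± 3 = Days 5 to 11 = 4 to 10 days after the dose.
- Day 8 visit: 8 ± 1 = Days 7 to 9 = 6 to 8 days after the dose.
- Monkey increases: 5 to 7 days after the dose = Days 6 to 8.
- Monkey return to baseline: 14 days after the dose = Day 15, which is 4 days after the sampling window closes.

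**2. Assumed profile.** The anchors are the monkey times in Section 2.2.3 and the monkey fold-changes in Section 2.3 (sCD25 F = 10, lymphocytes F = 2). The share of the peak response at t days after the dose is assumed to be:

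- w = t/5 for t < 5
- w = 1 for t from 5 to 7
- w = (14 − t)/7 for t > 7

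The fold-change over baseline is 1 + (F − 1)w for a linear shape, or F^w for a log-linear shape.

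**3. Spread of a single reading**

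sCD25:
- Day 5 (t = 4, w = 0.8): linear 1 + 9 × 0.8 = 8.2; log-linear 10^0.8 = 6.31.
- Days 6 to 8 (w = 1): 10.
- Day 9 (t = 8, w = 6/7 = 0.86): linear 8.71; log-linear 7.20.
- Day 11 (t = 10, w = 4/7 = 0.57): linear 6.14; log-linear 3.73.

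| Marker | Window | Linear, max/min | Log-linear, max/min |
|---|---|---|---|
| sCD25 | ± 3 days | 10/6.14 = 1.63 | 10/3.73 = 2.68 |
| sCD25 | ± 1 day | 10/8.71 = 1.15 | 10/7.20 = 1.39 |
| Lymphocytes | ± 3 days | 2/1.57 = 1.27 | 2/1.49 = 1.35 |
| Lymphocytes | ± 1 day | 2/1.86 = 1.08 | 2/1.81 = 1.10 |

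**4. Effect on a comparison of two cohorts.** Two cohorts with identical true response were simulated. Each subject's sampling day was drawn uniformly over the window (100,000 repeats). The table gives the 95th percentile of the ratio of geometric means (larger over smaller) due to timing alone, as linear to log-linear.

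| Marker | Subjects per cohort | ± 3 days | ± 1 day |
|---|---|---|---|
| sCD25 | 3 | 1.32 to 1.73 | 1.10 to 1.25 |
| sCD25 | 6 | 1.21 to 1.50 | 1.07 to 1.18 |
| Lymphocytes | 3 | 1.15 to 1.18 | 1.05 to 1.07 |
| Lymphocytes | 6 | 1.10 to 1.13 | 1.04 to 1.05 |

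The mean difference between cohorts was zero to within simulation error in every case. The window adds variance, not bias.

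**5. Which measures are exposed.** Lymphocyte counts are part of the hematology differential, scheduled on Days 1 to 5, 8, 11 and 15 of Cycles 1 and 2 in Table 1. They have their own fixed-day course. Flow cytometry, immune-function assays and cytokines have no such backup in the schedule text.

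**The case against.** Several points against the concern are sound.

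- **No confounding is shown.** A reader might infer that the window mixes dose with sampling time. That needs the sampling day to differ by dose level, and every cohort has the same window. What remains is noise and chance imbalance.
- **The monkey data are limited.** A reader might infer that the signal rises and falls within Days 5 to 11, or that a Day 5 sample precedes the rise. Section 2.2.3 reports when increases were observed, not when they began, and reports return to baseline only at 14 days. The data support a peak inside the window and, by inference, a partial decline by Day 11.
- **The modelled marker may not be the one measured.** Section 6.8.1 covers cell populations, activation and immune function and does not name sCD25. Here sCD25 stands in for a short-lived immune signal.
- **The two footnotes need not conflict.** A specific tolerance for one sample can sit beside a general visit window. It is loose, not contradictory.
- **The dose-selection link is permissive.** Section 4.1.2.2 says only that biological effect may be used, and no dose comparison of biomarkers is defined. On-treatment biopsies also inform immune activation, and Section 4.1.2.1 allows additional cohorts of up to 12 subjects.
- **Footnote w governs Part 2.** That part starts after the dose is chosen, so its window cannot affect that choice.

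These points limit the size of the concern. They do not supply a reason for the wider window, and they do not replace the missing rule on actual sampling day. The Laboratory Manual may require collection times to be recorded, but it is not among the documents.

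**Conclusion.** The point stands as a cheap improvement in precision, not as a flaw that threatens the trial. The draw may be taken over 7 days (Days 5 to 11) when the visit it belongs to is allowed 3 (Days 7 to 9). The protocol's own animal data suggest that the response may change over that span.

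On the assumed profiles, the tighter window cuts the possible timing shift in one sCD25 reading from about 1.6 to 2.7-fold to about 1.15 to 1.4-fold. For two cohorts of 3 with no true difference, the 95th percentile of the chance ratio falls from 1.32 to 1.73 down to 1.10 to 1.25.

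These figures are illustrative. They assume that the human time course resembles the monkey's, that the profile has the shapes given, and that all days in the window are equally likely. If most sites draw at the Day 8 visit anyway, the real noise is smaller. The listed dose steps are 2-fold, but the documents give no dose-response slope. They therefore cannot show that timing noise would hide or create a dose effect large enough to change the recommended dose. The exposure lies mainly in flow cytometry, cytokine and immune-function measures.

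**What to change.** 1. In Table 1 footnote x, set the post-dose biomarker draw to Day 8 ± 1 day, matching footnote a. Align Table 2 footnote w for consistency between the two parts.
2. In protocol Section 6.8.1, require the date and actual time of each blood biomarker sample, as Section 6.6 does for PK.
3. In SAP Section 12, state that post-dose biomarker results are analysed by actual days since the last dose. Flag samples outside Days 7 to 9 and keep them in the data. Add a sensitivity analysis restricted to in-window samples. Excluding them outright would discard scarce data in cohorts of 3.

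The cost is two footnote edits and a few sentences. No visit or blood draw is added. The downside is slightly less scheduling flexibility for one draw at a visit that already takes place.

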**Table 2: Schedule of Visits and Procedures Dose Expansion (Phase 2)**

Assessment Period	Screening	Cycle 1 and Cycle 2									Cycle 3 and Beyond			Post-Treatment		
		Day -28 to 1	Day 1	Day 2	Day 3	Day 4	Day 5	Day 8	Day 11	Day 15	Day 22 b	Day 1	Day 8	Day 22 b	End of Treatment (+10 days)	Follow-up 3 mo
Informed consent c	X															
Inclusion/exclusion criteria	X	X														
Demographics	X															
Medical/cancer history d	X															
Medication history e	X															
Physical examination f	X	X					X		X g	X	X	X	X	X		
Vital signs h	X	X	X	X	X	X	X	X	X g	X	X	X	X	X	X	
ECOG performance status	X											X				
ECG i	X	X	X	X	X	X	X	X	X g	X	X	X	X	X		
ECHO j	X													X		
Pregnancy test k	X	X									X			X		
Hematology l	X	X	X	X	X	X	X		X g	X	X	X	X	X	X	
Serum chemistry m	X	X			X		X		X g	X	X	X	X	X	X	
Coagulation n	X	X			X		X		X g	X	X	X	X	X	X	
Additional labs o	X								X g		X o			X		

## Footnotes:

- a. The acceptable visit window is + 1 day for Day 11 and  $\pm 1$  day for Day 8 and Day 15 and  $\pm 7$  days for the follow-up visit post-treatment. Visits may be skipped or postponed if prospectively identified by the Investigator (e.g., national holidays, subject holidays). If Day 4 visit is missed then Day 4 assessments must be done at the next in clinic visit. All procedures and examinations should be performed before the administration of study drug(s), except as indicated below.
- b. Assessments only applicable if dosing cycle is changed to 28-day cycle.
- c. The Institutional Review Board (IRB)-approved informed consent form (ICF) must be signed before any study-specific procedures or examinations are performed.
- d. An event occurring after the subject has provided informed consent, but before the first dose of study treatment, will be collected as medical history unless the event is either new and attributed to protocol-mandated procedures by the Investigator OR there is a significant change in the rate of occurrence or an increase in the severity of the pre-existing condition which is judged to be clinically important and attributed to the protocol-mandated procedures by the Investigator. Any new or clinically significant changes in the subject's medical and/or cancer history that occur immediately after the first dose of drug will be recorded as AEs.
- e. Include prior cancer treatments: previous immunotherapy, chemotherapy, targeted therapy, radiation, OTC medications, herbs and dietary supplements
- f. Physical examinations at screening/baseline, at day 1 of each cycle, and at end of treatment should be complete assessments (evaluate all major organ systems, including the following categories: general, head, eyes, ears, mouth/throat, neck, heart, lungs, abdomen, lymph nodes, joints, extremities, integumentary, neurologic, and psychiatric). Other examinations may be focused, at the discretion of the Investigator, to identify changes from baseline or evaluate changes based on the subject's clinical symptoms. Weight is to be reported at each visit, height at screening/baseline visit only.
- g. Assessments not applicable if dosing cycle is changed to 14-day cycle.
- h. Vital signs include temperature, pulse, respiration, systolic and diastolic blood pressure, and oxygen saturation. Monitor the subject for 1 hour postdosing and record vital signs at the end of the hour. If a subject should experience a Grade  $\geq 2$  infusion reaction or hypotension during study visit subject may be monitored for 24 hours. Per clinical judgment additional monitoring might be implemented.
- i. A 5-minute summary ECG will be performed for all subjects at screening and during the 5 minutes prior to the time points of predose, 0.5 hr  $\pm$  5 min., 3 hr  $\pm$  10 min, and 6 hr + 2 hr on Day 1 of Cycles 1 and 2 and on Days 2, 3, 4, 5, 8, 11, and 15 of Cycles 1 and 2. A 5-minute summary ECG starting 5 minutes before the predose time point will be performed on Days 1 and 8 of Cycle 3 and beyond, including EOT. Frequency of ECGs may be increased if clinically indicated. Prior to performing ECGs, subjects should rest in the supine position for at least 5 minutes. All ECGs should be taken prior to the PK draw.
- j. Stress echocardiogram (either exercise or nuclear) will be performed for all subjects within 60 days prior to Cycle 1 Day 1 and at End of Treatment to assess for cardiac function and left ventricular ejection fraction (LVEF). At the discretion of the Investigator, patients who are unable to perform a stress echocardiogram may instead have a MUGA scan or TTE. The same assessment method should be used for the same subject throughout the study.
- k. For women of childbearing potential, serum  $\beta$ -HCG pregnancy test is required at screening. Urine or serum pregnancy tests to be performed on Day 1 of each subsequent cycle and EOT. A pregnancy test does not need to be performed on women who are postmenopausal for at least 1 year or surgically sterile for at least 3 months before signing the ICF.

- l. Hematology performed at the indicated times by a central laboratory: red blood cell (RBC) count, hemoglobin (Hgb), hematocrit (Hct), mean corpuscular volume (MCV), platelet count, white blood cell (WBC) count, and WBC differential (neutrophils, lymphocytes, monocytes, eosinophils, and basophils), mean corpuscular hemoglobin (MCH), mean corpuscular hemoglobin concentration (MCHC) ([Appendix 1](#)). If hematology demonstrates CTCAE grade 3/4 cytopenias, increase frequency to daily monitoring as clinically appropriate. Hematology assessments scheduled for the day of study drug dosing must be available and assessed for toxicity before dosing. The sampling for hematology assessment can be drawn up to 24 hours prior to dosing.
- m. Serum chemistry performed at the indicated times by a central laboratory: sodium, potassium, calcium, chloride, creatinine, calculated creatinine clearance (Cockcroft-Gault), total bilirubin, albumin, alkaline phosphatase, CO2 or bicarbonate, lactate dehydrogenase (LDH), aspartate aminotransferase (AST), alanine aminotransferase (ALT), glucose, blood urea nitrogen (BUN), total protein (TP), gamma-glutamyl transferase (GGT), and uric acid ([Appendix 1](#)).
- n. Coagulation performed at the indicated times by a central laboratory: partial thromboplastin time and prothrombin time ([Appendix 1](#)).
- o. Additional tests performed at screening, on Day 15 of Cycle 1 and 2, and at End of Treatment: thyroid stimulating hormone, lipase, amylase, free thyroxine (T4), creatine kinase, HLA typing (only at screening) and on Day 1 beginning from Cycle 4 ([Appendix 1](#)).
- p. Microscopy is required only to follow-up clinically significant urine dipstick findings. List pH, specific gravity, protein, glucose, ketones, bilirubin, blood, and leukocyte esterase ([Appendix 1](#)).
- q. Serology tests include hepatitis B surface antigen (HBsAg), hepatitis C virus antibody (anti-HCV), and human immunodeficiency virus (HIV) antibody ([Appendix 1](#)).
- r. Unstained formalin-fixed, paraffin embedded, archival tumor tissue sections on slides are acceptable.
- s. One pre-treatment tumor tissue biopsy will be collected during screening (Cycle 1 Day 1 – 28 days). If a pre-treatment biopsy was collected within 28 days, tumor section can be provided. One on-treatment tumor tissue biopsy will be collected at Week 3 (7 to 1 days prior to Cycle 2 Day 1). An additional tumor tissue biopsy may be collected at the time of progression. All tumor biopsies will be collected from the same non-target lesion, if feasible. Twenty tumor biopsies will be collected. Exceptions will be made with Medical Monitor approval for tumors that are inaccessible.
- t. The screening immunogenicity sample should be drawn within 14 days prior to Cycle 1 Day 1. No immunogenicity sample will be drawn at pre-dose on Cycle 1 Day 1. Immunogenicity samples will be drawn at pre-dose on Cycle 2 Day 1, pre-dose on Day 1 of all odd-numbered cycles thereafter (e.g., Cycles 3, 5, 7, etc.), and at End-of-Treatment and Follow-up.
- u. Tumor assessment at screening then every 8 weeks ( $\pm$  7 days) and End-of-Treatment (unless scan done within 4-weeks). To ensure comparability, the baseline radiographs/scans and subsequent radiographs/scans to assess response should be performed using identical techniques. In the event of a partial response (PR) or complete response (CR), confirmatory radiographic imaging should be completed at least 4 weeks from imaging showing a CR or PR. If the subject discontinues treatment for a reason other than Progressive Disease, imaging will be conducted every 3 months until progressive disease is noted or start of new treatment.

- v. Any new or clinically significant changes in the subject's medical and/or cancer history that occur immediately after the first dose of drug will be recorded as AEs. All AEs, including serious AEs (SAEs), will be recorded immediately after the first dose of study drug until 30 days after the last dose of study medication. An SAE related to study procedures or study conduct must be reported to Nektar Therapeutics if it occurs prior to first dose of study drugs. SAEs must be reported as described in Section 8.7 of the protocol. Treatment-related AEs ongoing at the post-treatment visit should be followed to resolution or until the Investigator considers them "chronic" or "stable".
- w. Biomarker sample drawn prior to dose on Day 1 and on Day 8 ± 3 days. In addition, biomarker samples will be collected prior to dose on Day 1 of Cycle 3 and all odd-numbered cycles thereafter (e.g., Cycles 3, 5, 7, etc.). If the optional tumor biopsy at disease progression is collected, collect an additional biomarker sample at the same time.
- x. Stool sample to be collected prior to Cycle 1 Day 1.
- y. Blood samples (2 mL) for PK analyses will be collected in all cycles, with more intense sampling in Cycles 1 and 2. PK sample times are as follows: Cycles 1 and 2 Day 1: predose, end of administration (EOA ± 2 min), 0.5 hr ± 5 min, 3 hr ± 10 min, 6 hr + 2 hr, and 2, 3, 4, 5, 8, 11, and 15 days postdose. Cycle ≥ 3: predose, EOA ± 5 mins, Day 8 and End of Treatment.
- z. In the event of a possible study drug-related SAE throughout the study, additional PK blood samples will be drawn as close to the event as possible to help characterize any possible relationships between drug exposure and the clinical event.
- aa. Administer at least 2 liters of fluid (IV or self-administered orally [e.g., fluid containing electrolytes]) for Days 1 to 5 of every cycle. Advise subjects to restrain from strenuous activity and avoid long hot showers and saunas for Days 1 to 5 of every cycle. A Patient Wallet Card is available that contains important safety information.
- bb. Administer NKTR-214 at the subject's assigned dose level as an intravenous infusion over 15 min ± 5 min.

